#### **7.1.3. Adverse Events**

All AEs will be coded using MedDRA. Summaries will be presented in the overall treatment period (titration plus maintenance treatment period) for all AEs (overall and by severity), AEs determined by the investigator to be treatment-related, serious AEs, AEs causing discontinuation from the study, non-serious AEs, AEs leading to dose reduction, and AEs leading to dose suspension. In addition, all AEs will be summarized separately for the titration period, maintenance treatment period, and follow-up period.

All AEs in the overall treatment period will be summarized by strong CYP2D6 inhibitor status (Yes/No), poor CYP2D6 metabolizer phenotype status (Yes/No), impaired CYP2D6 function

status (Yes/No), baseline use of DRA status (Yes/No), and background comorbid illness type. In addition, serious AEs and AEs by severity will be summarized by impaired CYP2D6 function status.

The incidence of adverse events will be summarized using descriptive statistics by system organ class and preferred term. Patients are counted only once in each system organ class category and only once in each preferred term category. For all AEs in the overall treatment period, the event rate will also be presented. The event rate is defined as  $100 * (\text{total number of AEs} / \text{patient years of treatment in Parts A and B combined})$ . Treatment-related adverse event summaries will include adverse events with possible, probable, definite, or missing relationship to study drug. For the summaries by severity, patients are counted at the greatest severity only once in each system organ class category and only once in each preferred term category.

The Standard MedDRA Queries (SMQs) of depression (excl suicide and self injury), suicide/self-injury, akathisia, Parkinson-like events, and Torsade de pointes/QT prolongation AEs, and somnolence and sedation AEs of interest as specified in [Appendix A](#) will be summarized using descriptive statistics. In addition, time to first SMQ AE or AE of interest will be presented using Kaplan-Meier curves for each SMQ AE or AE of interest. For this analysis, patients who do not experience the event will be censored at the end of treatment in Parts A and B combined.

In addition, the exposure-adjusted incidence rate (EAIR) of AEs in the overall treatment period will be presented for the overview of AEs, AEs by SOC and preferred terms, and the SMQ summaries. EAIR is calculated as the number of patients with an AE divided by patient-years of treatment. For calculating patient years, patients with an AE contribute with treatment exposure up to the day of their first AE, patients without an AE contribute their entire treatment duration in Parts A and B combined as described above for the censoring if patients do not experience an event.

The EAIR for all AEs in the overall treatment period and for SMQ categories will be summarized by the time periods of <15 weeks,  $\geq 15$  to <54 weeks,  $\geq 54$  to <106 weeks,  $\geq 106$  to <158 weeks, and  $\geq 158$  weeks using descriptive statistics.

All AEs in the overall treatment period that occurred in  $\geq 4\%$  of patients will be summarized by preferred term using descriptive statistics.

Listings for AEs leading to death, serious AEs, AEs causing discontinuation, AEs leading to dose reduction, and AEs leading to dose suspension will be presented.

#### **7.1.4. Deaths**

If any patient dies during the study all relevant information will be discussed in the patient's narratives included in CSR.

#### **7.1.5. Clinical Laboratory Tests**

Summary statistics for serum, chemistry, hematology, and urinalysis laboratory tests will be presented at baseline of this study and each Part A visit that this is measured using standard international units. Serum chemistry laboratory tests will also be presented using conventional units. Laboratory tests values and changes from baseline of this study to each visit will be

summarized using descriptive statistics. Shifts (below, within, and above the normal range) from baseline of the parent study to each Part A visit will be summarized using patient counts.

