### 8.3. Safety Analyses

Safety and tolerability will be assessed throughout the study by monitoring the following parameters:

- Adverse events
- Clinical laboratory tests
- Physical examination
- Vital signs
- 12-lead ECGs
- UPDRS – Motor Examination
- BARS
- HADS
- C-SSRS
- ESS
- MoCA®

Safety data will be summarized descriptively for the overall population and based on prior treatment (SD-809 or placebo) in the parent study. Descriptive statistics will be calculated for quantitative data and frequency counts and percentages will be provided for categorical data. Descriptive statistics of change-from-baseline will use the Baseline from the present study (SD-809-C-20 Baseline).

The nature, frequency, and severity of adverse events will be tabulated for all subjects combined and by treatment. Baseline, within study, end of study, and change-from-baseline values for

clinical laboratory evaluations and vital signs will be summarized as appropriate. Treatment-emergent adverse events and laboratory, vital sign, and ECG parameters will be summarized. In addition, change from baseline will be summarized for laboratory and vital sign parameters. Shift tables will be provided for clinical laboratory results. ECG results will be classified as normal and abnormal and summarized.

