#### **8.4. Safety Endpoints**

The following safety endpoints will be assessed in Part A:

- Incidence of adverse events, serious adverse events, severe adverse events, drug-related adverse events, adverse events leading to withdrawal during the following periods:
  - Overall
  - During titration
  - During long-term treatment
- Observed values and changes from baseline in clinical laboratory parameters (hematology, chemistry, and urinalysis)
- Observed values and changes from baseline in vital signs
- Observed values in ECG parameters and abnormal findings
- Number of subjects with on-treatment QTcF values >450 ms, >480 ms, >500 ms, or a change from Baseline in QTcF of >30 ms or >60 ms
- Observed values and changes in UPDRS Part III (motor examination), BARS, HADS, C-SSRS, ESS, and MoCA©
- Duration of time to achieve stable dosing of SD-809

The following secondary safety endpoints will be assessed in Part B:

- Incidence of adverse events, serious adverse events, severe adverse events, drug-related adverse events, and adverse events leading to withdrawal
- Observed values and changes from start of randomized withdrawal in clinical laboratory parameters (hematology, chemistry, and urinalysis)
- Observed values and changes from start of randomized withdrawal in vital signs
- Observed values in ECG parameters and abnormal findings
- Number of subjects with on-treatment QTcF values >450 ms, >480 ms, >500 ms, or a change from Baseline in QTcF of >30 ms or >60 ms
- Observed values and changes in UPDRS Part III (motor examination), BARS, HADS, C-SSRS, ESS, and MoCA©

The following secondary safety endpoints will be assessed in Part C:

- Secondary safety endpoints:
  - Incidence of adverse events, serious adverse events, severe adverse events, drug-related adverse events, and adverse events leading to withdrawal from start of Part C
  - Observed values and changes in vital signs from start of Part C
  - Observed values and changes in C-SSRS from start of Part C
  - Observed values in ECG parameters and abnormal findings from start of Part C

- Number of subjects with on-treatment QTcF values >450 ms, >480 ms, >500 ms, or a change from Baseline in QTcF of >30 ms or >60 ms from start of Part C

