C-SSRS 	**		X		X		X	X	X	X	X	X	X	X	X	X	X	X	X	X	X		X								
ESS	**		X		X		X	X	X	X	X	X	X	X	X	X	X	X	X	X	X		X 								
CGIC					X		X	X	X	X	X	X	X	X	X	X	X	X	X	X	X										
PGIC					X		X	X	X	X	X	X	X	X	X	X	X	X	X	X	X										
MoCA ©	X						X	X	X	X	X	X	X	X	X		X		X												
Modified CDQ-24	X						X	X	X	X	X				X				X												
Dispense/Order Study Drug 	X	X	X	X	X	X	X	X	X	X	X	X	X	X	X	X	X	X	X	X		X 	X 								
Assess Study Drug Accountability/ Compliance				X		X		X	X	X	X	X	X	X	X	X	X	X	X	X											
Assess AEs	*		X	X	X	X	X	X	X	X	X	X	X	X	X	X	X	X	X	X	X	X	X								
Assess Concomitant Meds	*		X	X	X	X	X	X	X	X	X	X	X	X	X	X	X	X	X	X	X	X	X								
Evaluate Dyskinesia Control (patient/ caregiver)			X	X	X	X	X	X	X	X	X	X	X	X	X	X	X	X	X	X	X	X	X								

SCHEDULE OF EVENTS (Part A) KEY

- [V] Clinic Visit
- [TC] Telephone Contact
- [ET] Early Termination Visit
- [U] Urine pregnancy test for women of childbearing potential only

Abbreviations: AEs, adverse events; AIMS, Abnormal Involuntary Movement Scale; BARS, Barnes Akathisia Rating Scale; CDQ-24, Craniocervical Dystonia Questionnaire; CGIC, Clinical Global Impression of Change; C-SSRS, Columbia Suicide Severity Rating Scale; ECG, electrocardiogram; ESS Epworth Sleepiness Scale; HADS, Hospital Anxiety and Depression Scale; MoCA©, Montreal Cognitive Assessment; PGIC, Patient Global Impression of Change; PK, pharmacokinetics; SAE, serious adverse event; UA, urinalysis; UPDRS, Unified Parkinson’s Disease Rating Scale.

† All stable patients will be invited to participate in Part B after Amendment 06 implementation regardless of current study week. Patients will need to be on a stable dose of SD-809 and any concomitant dopamine receptor antagonist for a minimum of 4 weeks before starting the Double-Blind, Randomized Withdrawal Period.

† After Informed Consent is obtained, prior data from the parent study will be used in this study as part of screening information as detailed in the informed consent/assent.

‡ Data from the Week 13 evaluation of the parent study will provide some of the Baseline data for the present study, although such data will not become available for this study until informed consent/assent has been provided.

§ May be performed up to 30 days in advance of Baseline

\* Data (Week 12 or earlier) from the parent study will be used in this study as part of screening information.

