### **4.2. Specification of Baseline Values**

Baseline of this study is the last observed data on or prior to the first dose of drug in the present study (SD-809-C-20). Some of the data used for baseline of this study will come from the parent study (see [Table 1](#)). For baseline data that is coming from the parent study, baseline of this study will be the last observed data collected during the follow-up phase of the parent study. If data are not collected or are missing during the follow-up period in the parent study, then baseline of this study will be the last observed data on or prior to the first dose of drug in the parent study.

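### Part A laboratory shifts are counted from the parent-study baseline, so an abnormality that arose on parent-study placebo and persisted appears as a shift on SD-809

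*SAP*

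**What the plan says.** The protocol. Section 8.3 states: "Descriptive statistics of change-from-baseline will use the Baseline from the present study (SD-809-C-20 Baseline". The same section adds "Shift tables will be provided for clinical laboratory results", with no reference visit. Section 8.4 lists for Part A "Observed values and changes from baseline in clinical laboratory parameters (hematology, chemistry, and urinalysis".

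The SAP. Section 7.1.5 uses two references. For changes: "Laboratory tests values and changes from baseline of this study to each visit will be" summarized descriptively. For shift tables: "Shifts (below, within, and above the normal range) from baseline of the parent study to each Part A visit". ECG shifts (7.1.7) and C-SSRS shifts (7.1.11) both start from the baseline of this study.

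SAP 4.2 opens with a general rule: "Baseline of this study is the last observed data on or prior to the first dose of drug in the present study". For data taken over from the parent study, it then uses the last value from the parent follow-up phase. If there is none, "then baseline of this study will be the last observed data on or prior to the first dose of drug in the parent study".

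In the Part A schedule (SAP Table 1), the chemistry, hematology and urinalysis row has no draw at the C-20 Baseline. It carries only the single asterisk, defined as "Data (Week 12 or earlier) from the parent study will be used in this study as part of screening information". It does not carry the double asterisk that marks parent Week 13 data taken as Baseline.

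Part A safety tables are shown by parent-study treatment and overall (SAP 7.1.1). SAP Section 9 lists one change from the protocol, which concerns ECG variables.

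**The concern.** Everyone in Part A takes SD-809, so a normal-to-abnormal shift will be read as something that happened on the drug. For prior-SD-809 patients the pre-parent value supports that reading over their whole exposure, because it is their last value before any SD-809. For prior-placebo patients it does not. Their parent-study period was also free of SD-809, yet anything that turned abnormal during it and persisted is counted as a shift in Part A. Prior treatment is the only split these tables offer, so the misattribution falls in one of the two columns and carries into the overall column. Long-term safety is the study's first objective, and nothing in the SAP explains why laboratory shifts use a different reference from the other shift tables.

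**Working it through.** The plan states no figure for this point, so there is none to reproduce.

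**1. Which value each rule selects for a laboratory test**

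| Rule | Value selected |
|---|---|
| Protocol 8.3 (changes) | C-20 Baseline, at which no lab is scheduled |
| SAP 4.2, first sentence | Latest lab on or before the first C-20 dose, so a late parent-study lab if one exists |
| SAP 4.2, parent-sourced data | Parent follow-up lab, if collected |
| SAP 4.2, fallback | Last lab on or before the first parent dose |
| SAP 7.1.5 (shifts) | Parent-study baseline |

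The last row holds whatever the parent studies collected. Whether changes also reach the pre-parent value depends on whether parent follow-up labs exist. The single asterisk suggests that they do not, but it shows only what this study imports.

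**2. How much of the interval precedes SD-809 in prior-placebo patients**

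The C-20 Baseline coincides with parent Week 13, so the parent baseline is about 13 weeks before the first C-20 dose, or more if the lab was drawn at parent screening. The first Part A labs are at Week 6. That shift spans about 13 + 6 = 19 weeks, of which 13/19 = 68% precedes any SD-809. At Week 158 the share is 13/(13 + 158) = 8%.

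**3. Illustrative size with no drug effect**

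All inputs are assumed. Let Y0, Y1 and Y2 be the pre-parent, last on-placebo and Part A values, normal with SD 1, and let U = 1.645 be the upper limit (95th percentile). A drift d is added to both Y1 and Y2. The correlations (Y0Y2, Y1Y2, Y0Y1) are set A = (0.65, 0.75, 0.70) and set B = (0.75, 0.80, 0.78).

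- SAP shift rate: P(Y0 ≤ U, Y2 > U)
- Alternative, from the last pre-SD-809 lab: P(Y1 ≤ U, Y2 > U)
- Net excess = P(Y0 ≤ U, Y1 > U, Y2 > U) − P(Y0 > U, Y1 ≤ U, Y2 > U)

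| Set, d | SAP | Alternative | Net excess | SAP shifts already high at Y1 |
|---|---|---|---|---|
| A, 0 | 3.25% | 2.81% | 0.44 | 32% |
| A, 0.1 | 4.13% | 3.31% | 0.81 | 35% |
| A, 0.2 | 5.18% | 3.86% | 1.32 | 38% |
| B, 0 | 2.81% | 2.53% | 0.27 | 34% |
| B, 0.1 | 3.65% | 2.97% | 0.68 | 37% |
| B, 0.2 | 4.67% | 3.47% | 1.20 | 40% |

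The net excess is in percentage points and is computed before rounding. The last column is gross. Under the alternative reference, 16% to 26% of counted shifts were already high at Y0, and the net column allows for that.

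**4. Sensitivity to the assumptions**

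A second model has U = 1.96, equal within-patient correlation of 0.5 to 0.9 at all visits, and a persistent mean-zero drift with SD 0 to 0.6. Without drift the net excess vanishes (1.68% against 1.68% at correlation 0.7). At correlation 0.9 and drift SD 0.6 it is 3.25% − 1.48% = 1.77 points. The gross share already high before SD-809 runs from 15% to 62%.

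**5. Changes, if the fallback applies**

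The SD of change is √(2(1 − r)). For set A, √0.70/√0.50 = 1.18. For set B, √0.50/√0.40 = 1.12. Changes would be 12% to 18% more variable, and the mean change would contain the whole drift d.

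**The case against.** The strongest defence is that the SAP's choice is visible and coherent. It gives both columns an untreated reference at the same point in time, and for prior-SD-809 patients it is the natural one. Protocol 8.3 attaches the C-20 Baseline to change statistics, and its shift-table sentence names no baseline. The synopsis leaves details to the SAP, and the SAP says that it prevails, with differences explained in the study report. The tables are descriptive and no test uses them.

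Much of this stands. A reader might infer that the SAP contradicts an explicit protocol rule for shifts. The text does not go that far: the protocol gives one baseline for change and is silent on shifts, and the SAP fills the gap with an unexplained choice that it applies to no other Part A shift table.

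A reader might also infer that every abnormality a prior-placebo patient had before SD-809 is counted as a shift. It is not: one already present at the parent baseline stays abnormal-to-abnormal.

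Nor do the documents establish that laboratory changes use the pre-parent value. That requires the parent studies to have collected no follow-up labs, and their protocols are not available here. The existence of a late on-placebo lab is likewise unconfirmed.

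What the defence does not answer is the prior-placebo column, where a common time point is bought by counting events from an SD-809-free period as shifts on SD-809.

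**Conclusion.** The point holds for shifts as written, and conditionally for changes. In prior-placebo patients, laboratory abnormalities that arise after the parent baseline and persist are tabulated as Part A shifts although they preceded SD-809. For changes, SAP 4.2 is in tension with itself: its first sentence selects the latest lab before the first C-20 dose, while its fallback selects the pre-parent one.

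The size is unknown, because the documents give neither abnormality nor drift rates. On the main set of assumptions the net excess of high shifts is about 0.3 to 1.3 percentage points per analyte and visit; the second set gives 0 to 1.8. The 32% to 40% of shifts already high before SD-809 could be read as the inflation of the table. It is not, because most or part of it is offset by patients who were high at the parent baseline and normal later. The fault is mainly one of attribution in one column of a descriptive table, and correcting it is a low-priority but cheap improvement.

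**What to change.** In SAP 4.2 and 7.1.5, name one laboratory reference for both changes and shifts: the last available value before the patient's first SD-809 dose. For prior-placebo patients this is the latest imported parent-study lab; for prior-SD-809 patients it is the pre-dose parent value. Label it as that, not as the baseline of this study. Footnote that the reference visit and the interval differ by prior treatment, so the two columns do not cover equal time and the overall column mixes them. Keep the parent-baseline shift table as labelled supplementary output if it is wanted. List the departure from protocol 8.3 in SAP Section 9.

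The cost is SAP wording and a re-derived baseline flag on parent-study labs that the schedule already brings in. No new data are needed. The one real downside is the unequal reference timing, which the footnote discloses.

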#### **7.1.6. Vital Signs**

Summary statistics for resting heart rate and blood pressure, respiration rate, temperature, and weight will be presented at baseline of this study and at each Part A visit that these are measured. Summary statistics for orthostatic heart rate and blood pressure will be presented at baseline of this study and each Part A visit that this is measured. Vital signs values and changes from baseline to each visit the vital sign is measured will be summarized using descriptive statistics.

Orthostatic changes in heart rate and orthostatic changes in blood pressure vital signs values are calculated as the standing minus supine value at the same visit.

#### **7.1.7. Electrocardiogram**

Shifts (normal, abnormal not clinically significant, and abnormal clinically significant) from baseline of this study to each Part A visit that this is measured will be summarized using patient counts.

The number of patients with postbaseline QTcF values >450 ms, >480 ms, >500 ms, or a change from baseline in QTcF of >30 ms or >60 ms, PR interval values >200 ms, QRS duration values >100 ms, and QT interval values >500 ms will be summarized using descriptive statistics. This summary will be repeated for patients who have a normal QTcF at baseline according to the protocol definition.

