## 2.2. Primary and Secondary Measures and Endpoints

### 2.2.1. Safety Measures and Endpoints

The safety measures and endpoints in Part A are as follows:

1. Incidence of AEs, SAEs, severe AEs, drug related AEs, AEs leading to withdrawal, AEs leading to dose reduction, AEs leading to dose suspension during the following periods: overall, during titration, and during long-term treatment
2. Observed values and changes from baseline in clinical laboratory parameters (hematology, chemistry, and urinalysis)
3. Observed values and changes from baseline in vital signs
4. Observed values in electrocardiogram (ECG) parameters and abnormal findings
5. Number of patients with on-treatment QTcF (Fridericia-corrected QT interval) values >450 ms, >480 ms, >500 ms, or a change from baseline in QTcF of >30 ms or >60 ms.
6. Observed values and changes in Unified Parkinson's Disease Rating Scale (UPDRS) Part III (motor examination), Barnes Akathisia Rating Scale (BARS), Hospital Anxiety and Depression Scale (HADS), Columbia-Suicide Severity Rating Scale (C-SSRS), Epworth Sleepiness Scale (ESS), and MoCA® (Montreal Cognitive Assessment)

The safety measures and endpoints in Part B (Randomized Withdrawal Period) are as follows:

1. Incidence of adverse events, serious adverse events, drug-related adverse events, and adverse events leading to withdrawal.
2. Observed values and changes from start of randomized withdrawal in clinical laboratory parameters (hematology, chemistry, and urinalysis)
3. Observed values and changes from start of randomized withdrawal in vital signs
4. Observed values in electrocardiogram (ECG) parameters and abnormal findings
5. Number of patients with on-treatment QTcF (Fridericia-corrected QT interval) values >450 ms, >480 ms, >500 ms, or a change from baseline in QTcF of >30 ms or >60 ms.
6. Observed values and changes in UPDRS Part III (motor examination), BARS, HADS, C-SSRS, ESS, and MoCA®

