## **7. SAFETY ANALYSIS**

### **7.1. Part A**

#### **7.1.1. General**

The safety population will be used for all safety summaries. Summaries will be presented by parent study treatment group and overall. Summaries will be presented for Parts A and B combined unless otherwise noted.

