#### **7.2.6. Electrocardiogram**

Shifts (normal, abnormal not clinically significant, and abnormal clinically significant) from the Pre-Withdrawal Visit to each Part B visit that this is measured will be summarized using patient counts.

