**9. CHANGES TO PROTOCOL SPECIFIED ANALYSES**

ECG variables at each visit will not be analyzed in this study.

**APPENDIX A. SMQ CATEGORIES ADVERSE EVENTS AND ADVERSE EVENTS OF INTEREST**Depression (excl suicide and self injury) (SMQ) – narrow search

Activation syndrome  
Adjustment disorder with depressed mood  
Adjustment disorder with mixed anxiety and depressed mood  
Agitated depression  
Anhedonia  
Antidepressant therapy  
Childhood depression  
Decreased interest  
Depressed mood  
Depression  
Depression postoperative  
Depressive symptom  
Dysphoria  
Electroconvulsive therapy  
Feeling guilty  
Feeling of despair  
Feelings of worthlessness  
Helplessness  
Major depression  
Menopausal depression  
Post stroke depression  
Postictal depression  
Postpartum depression

Suicide/self-injury (SMQ) – narrow search

Completed suicide  
Depression suicidal  
Intentional overdose  
Intentional self-injury  
Poisoning deliberate  
Self-injurious behaviour  
Self-injurious ideation  
Suicidal behaviour  
Suicidal ideation  
Suicide attempt

Akathisia (SMQ) – narrow and broad search

Akathisia  
Extrapyramidal disorder  
Hyperkinesia  
Hyperkinesia neonatal  
Motor dysfunction

Movement disorder  
Psychomotor hyperactivity  
Restlessness

Parkinson-like events (SMQ) – narrow and broad search

Action tremor  
Akinesia  
Bradykinesia  
Bradyphrenia  
Cogwheel rigidity  
Drooling  
Dysphonia  
Extrapyramidal disorder  
Freezing phenomenon  
Gait disturbance  
Hypertonia  
Hypertonia neonatal  
Hypokinesia  
Hypokinesia neonatal  
Masked facies  
Micrographia  
Mobility decreased  
Motor dysfunction  
Movement disorder  
Muscle rigidity  
Muscle tone disorder  
Musculoskeletal stiffness  
On and off phenomenon  
Parkinson's disease  
Parkinson's disease psychosis  
Parkinsonian crisis  
Parkinsonian gait  
Parkinsonism rest tremor  
Parkinsonism  
Parkinsonism hyperpyrexia syndrome  
Postural reflex impairment  
Postural tremor  
Resting tremor  
Tremor  
Tremor neonatal  
Walking disability

Somnolence and sedation – preferred terms

Sedation  
Somnolence  
Sopor  
Stupor

Lethargy

Torsade de pointes/QT prolongation (SMQ) – narrow and broad search

Cardiac arrest  
Cardiac death  
Cardiac fibrillation  
Cardio-respiratory arrest  
Electrocardiogram QT interval abnormal  
Electrocardiogram QT prolonged  
Electrocardiogram U-wave abnormality  
Electrocardiogram repolarization abnormality  
Long QT syndrome  
Long QT syndrome congenital  

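### The QTcF threshold endpoint is defined on treatment and listed separately for Part B, but the SAP counts postbaseline values by parent-study arm and plans no Part B threshold count by randomised arm

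*SAP*

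**What the plan says.** **The endpoint.** Protocol 8.4 lists, for Part A and again for Part B, "Number of subjects with on-treatment QTcF values >450 ms, >480 ms, >500 ms, or a change from Baseline in QTcF of >30 ms" or more than 60 ms. SAP 2.2.1 carries this over as item 5 in both of its lists: "Number of patients with on-treatment QTcF (Fridericia-corrected QT interval) values >450 ms, >480 ms, >500 ms", with the same two change categories. The second list is introduced by "The safety measures and endpoints in Part B (Randomized Withdrawal Period) are as follows".

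**The Part A (and combined) analysis.** SAP 7.1.7 plans "The number of patients with postbaseline QTcF values >450 ms, >480 ms, >500 ms", with the change categories and some PR, QRS and QT limits. SAP 7.1.1 governs the section: "Summaries will be presented by parent study treatment group and overall", and "Summaries will be presented for Parts A and B combined unless otherwise noted".

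**The Part B analysis.** SAP 7.2.1 says that Part B safety is presented by randomised withdrawal arm. For ECG, SAP 7.2.6 contains only "Shifts (normal, abnormal not clinically significant, and abnormal clinically significant) from the Pre-Withdrawal Visit" to each Part B visit.

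**The declared change.** SAP 9 has one line: "ECG variables at each visit will not be analyzed in this study".

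**The concern.** The endpoint and its analysis differ in three respects: the ECGs that qualify, the arms compared, and whether Part B is covered at all.

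The word *postbaseline* lets in any included ECG after baseline, whether or not the patient was taking SD-809. During the randomised withdrawal week half of the Part B patients are on placebo, and an ECG is taken at the end of that week. Grouping by parent-study arm cannot separate them, because parent-study assignment has nothing to do with assignment in the withdrawal period.

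The withdrawal week is the only randomised placebo control in this study. The protocol treats QTcF as a monitored risk: section 5.2.5 has a QTcF discontinuation rule, and section 6.7.1 requires extra ECGs after antipsychotic changes. A listed Part B QTcF count by randomised arm would therefore drop out without being declared.

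**Working it through.** No QTcF event rate or QTcF standard deviation appears in either document, so the check is mainly a comparison of sections.

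**1. Which ECGs enter the 7.1.7 count?** The shift paragraph of 7.1.7 is limited to Part A visits; the threshold paragraph is not. With no exception noted, the 7.1.1 default applies and Part B ECGs are included. SAP 4.5 removes unscheduled visits during Part B open-label treatment, so the count does not take in every postbaseline ECG.

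**2. Are any of these off drug?** Protocol 6.4 schedules a 12-lead ECG at both the Pre- and Post-withdrawal Visits. Under protocol 5.2.3, open-label SD-809 starts the day after the Post-withdrawal Visit. The placebo arm's ECG at that visit is therefore taken after a week, or up to 10 days, without SD-809. Elsewhere the choice of word makes little difference: the post-treatment clinic visit (protocol 6.6.1) has no ECG, and the Part B EOT ECG is taken as open-label treatment ends.

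**3. How many patients?** SAP 2.3 gives 143 randomised and SAP 2.4 gives 1:1 allocation, so 143 / 2 = 71.5, or about 71-72 on placebo. This is an upper limit, because some may have no Post-Withdrawal ECG. (The power quoted for 143 patients agrees with this split: the noncentrality is 1.4 / (2.9 × √(1/72 + 1/71)) = 2.89, and the two-sided t-test power is 81.8%, against a stated figure of approximately 80%.)

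**4. How far could the count move?** 7.1.7 counts patients, so the off-drug ECG changes a threshold count only if the patient exceeded that threshold on no other included ECG. Assume, purely for scale, that this holds for 1% to 10% of placebo patients:

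- 1%: 71.5 × 0.01 = 0.7 patients; 0.7 / 330 = 0.2 percentage points
- 10%: 71.5 × 0.10 = 7.2 patients; 7.2 / 330 = 2.2 percentage points

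The denominator is the approximately 330 patients planned for Part A. The rates are assumptions. The error can only add patients to the count.

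**5. Is the Part B endpoint counted anywhere by randomised arm?**

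| Reading of 7.1.7 | Placebo-week ECG | Part B threshold count by randomised arm |
|---|---|---|
| Parts A and B combined (7.1.1 default) | counted with on-drug ECGs | none |
| Part A only | not counted | none; Part B is counted nowhere |

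Neither reading supplies it. By contrast, SAP 7.2.4, 7.2.5 and 7.2.7 give values and changes from Pre-Withdrawal, by randomised arm, for laboratory tests, vital signs, UPDRS, BARS, HADS, ESS and MoCA.

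**6. What could the missing table show?** For a threshold with no events in 71 patients, the one-sided 95% upper bound is 1 − 0.05^(1/71) = 4.1%.

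**7. Reference value.** The Part B QTcF item speaks of change from baseline, while the Part B laboratory and vital-sign items use the start of randomised withdrawal. The SAP does not say which applies to a Part B change category.

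**The case against.** Much can be said for the plan.

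- **Part B ECGs are tabulated by arm.** The 7.2.6 shifts fall under 7.2.1. A reader might infer that the withdrawal-week ECGs are never compared; that is not so. Only the threshold and change-category counts are missing.
- **The number of placebo ECGs is not the size of the error.** A reader might take 71-72 as a count of false exceedances. It is a ceiling on the patients who have one such tracing; the distortion needs a sole exceedance at that visit.
- **Pooling is inferred.** It rests on the 7.1.1 default inside a section headed Part A. It is the likelier reading, but 7.1.7 does not state it.
- **On-treatment is not defined.** SAP 4.5 runs the overall treatment period through Part B EOT, so a programmer could treat the placebo week as treatment. That would soften the first limb, but it would not supply the Part B count.
- **The by-visit removal is declared.** SAP 9 states it openly. A reader might infer that by-visit ECG summaries must be restored or the observed-ECG endpoint deleted. Neither follows: that endpoint also covers abnormal findings, which the shift tables deliver.
- **No mean QTcF change or test was promised.** Both documents list ECG values, abnormal findings and threshold counts, summarised descriptively. Any claim about the precision of a mean difference would need an SD that the documents do not give. The discontinuation rule is per patient, and 7.1.7 counts patients at the same cut-offs.

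These points narrow the concern without removing it. Section 9 refers to ECG variables at each visit. A patient-level threshold count is not such a variable, and SAP 2.2.1 still lists it for Part B.

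**Conclusion.** Wrong as written, on a limited point. The endpoint in SAP 2.2.1 and protocol 8.4 is on-treatment and is listed separately for Part B. The only planned analysis is postbaseline, by parent-study arm and, under the default rule, pooled over both parts. The departure is not declared in SAP 9.

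The effect on the pooled count is probably small: 0.2 to 2.2 percentage points if 1% to 10% of placebo patients exceeded a threshold only at that visit, which is an assumed range. The larger loss is that a listed Part B safety endpoint is not reported by randomised arm. The primary AIMS analysis is unaffected.

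**What to change.** 1. **SAP 7.1.7:** replace *postbaseline* with *on-treatment*, define it as ECGs taken while receiving SD-809, and exclude the Post-Withdrawal ECG of patients randomised to placebo. State whether Part B ECGs are included.
2. **SAP 7.2.6:** add the listed QTcF threshold and change-category counts at the Post-Withdrawal Visit by randomised arm.
3. **Reference visit:** state whether the Part B change categories are measured from the baseline of this study or from the Pre-Withdrawal Visit.

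A descriptive change in QTcF from Pre- to Post-Withdrawal by arm would be an optional addition, since it is not a listed endpoint.

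The cost is a few lines of SAP text and one descriptive table. The ECGs are already scheduled and centrally read, so no new data collection is needed.
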